#### 4.8 Eligibility criteria

#### 4.8.1 Inclusion criteria

A patient is eligible for the study if all of the followings apply:

- a) Aged 18-80 years (inclusive)
- b) With chronic kidney disease (CKD)stage 3 to 5 (eGFR 60 to 0 mL/min/1.73m2 (inclusive)) Note: eGFR = estimated glomerular filtration rate
- c) Having provided informed written consent.

#### 4.8.2 Exclusion criteria

Any patient meeting any of the exclusion criteria will be excluded from study participation.

- 1) Known hypersensitivity to any component used in the study.
- 2) With inadequate hematologic function with: absolute neutrophil count (ANC) <1,500/μL OR platelets < 100,000/μL OR Hemoglobin < 8 g/dL
- 3) With impaired hepatic function with: serum bilirubin, aspartate aminotransferase (AST), alanine aminotransferase (ALT) or alkaline phosphatase (AKP), prothrombin time above and normal reference and serum albumin below normal reference range.
- 4) With hemoglobin A1c (HbA1c) > 8.0%
- 5) With serious prior or ongoing medical conditions (e.g. concomitant illness such as cardiovascular (e.g. New York Heart Association grade III or IV), hepatic e.g. Child-Pugh Class C), psychiatric condition, alcoholism, drug abuse), medical history, physical findings, ECG findings, or laboratory abnormality that in the investigators' opinion could interfere with the results of the trial or adversely effect the safety of the patient

- 6) Pregnant or lactating women or premenopausal with childbearing potential but not taking reliable contraceptive method(s) during the study period
- 7) With known history of human immunodeficiency virus (HIV) infection or any type of hepatitis
- 8) Judged to be not applicable to this study by investigator such as difficulty of followup observation
- 9) With any other serious diseases/medical history considered by the investigator not in the condition to enter the trial
- 10) Known or suspected abuse of alcohol or narcotics
- 11) With known history of cancer within past 5 years
- 12) With any autoimmune disease
- 13) With congenital kidney disease
- 14) With precancerous condition or with raised tumour markers like Alpha feto protein, Carcino embryonic antigen (CEA), C.A 19.9, C.A 125, Serum PSA above normal reference range.
- 15) Participants having a harvested total "Adipose Derived Stem Cell (ADSC)" count (in 5 ml SVF solution) less than 1 x 10^6 will be excluded from the study.

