4.1 Study design

Study Type: Interventional.

Primary Purpose: Treatment

Study Phase: Phase 1/Phase 2

Interventional Study Model: Parallel Assignment

Participants will be placed in either of the 2 groups, depending on

the number of harvested total stem cell count.

Those having a harvested total "Adipose Derived Stem Cell

(ADSC)" count (in 5 ml SVF solution) between 1 x 10^6 to 2 x

10^6 will be placed in "Group A".

13

Those having a harvested total "Adipose Derived Stem Cell (ADSC)" count (in 5 ml SVF solution) more than 2 x 10^6 will be placed in "Group B".

Both groups will be studied for Phase I/ Phase II trial by the proposed outcome measures over the stipulated time frame.

Those having a harvested total "Adipose Derived Stem Cell (ADSC)" count (in 5 ml SVF solution) less than 1 x 10^6 will be excluded from the study.

Number of Arms: 2

Masking: Triple (Participant, Care Provider, Outcomes Assessor)

Allocation: Non-Randomized

Enrollment: 31 [Anticipated]

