#### 4.7 Sampling technique & Recruitment of study subjects

Participants of the study will be recruited from the patients with CKD attending the Bangladesh Laser & Cell Surgery Institute & Hospital considering the eligibility criteria. The recruitment will be continued till the desired sample is drawn.

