#### 4.11 Outcome measures

#### **4.11.1 Primary Outcome Measure**

a) Incidence of minor adverse events (MAEs), serious adverse events (SAEs) which may be immediate, early or late - for Phase I [Time Frame: Week 48]

Minor adverse events (MAEs):

i) Pain from lipo-suction > 7 days (Early)

- ii) Fever > 7 days (Early)
- iii) Subcutaneous hematoma / abscess formation (Early)
- iv) Allergic reaction (Immediate)

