#### 6.3 Materials

- **a) Study population** According to sample size calculation 31 patients with established CKD will be recruited in the study over the estimated study period.
- **b) Equipment** "UNISTATIONTM" a specially designed medical device to satisfy diverse demands for various autologous cell therapies.

UNISTATION is a specially designed medical device to satisfy diverse demands for various autologous cell therapies with only one device. PRP, PRF isolation, and fat purification functions have been added to UNISTATIONTM.

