#### 7 **Procedure**

After harvesting the abdominal adipose tissue via liposuction SVF (stromal vascular fluid) are collected. Subsequently these are centrifuged in UNISTATIONTM, a centrifuge machine specifically manufactured for this purpose. Later it is mixed with collagenase solution and fat is separated. Stem cells containing SVF is collected after centrifugation. SVF is neutralized and washed with normal saline. Then it is washed with patient's own serum and normal saline. A sample is collected for cell counting by **Luna automated cell counter**. The final SVF is ready for subcutaneous or IV injection if 80-90% of cell remain viable, active and mobile.

As it is a closed door automatic procedure within a same machine, so after collection of 40ml of sub-cutaneous fat, all procedures are automated. So there is no chance of contamination. Steps are mentioned below.

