## **Final Step: Preparation for Injection**

To transfuse the final 5 ml of SVF to the patient through intravenous route. Before that to collect few drops of SVF sample for cell counting by Luna Stem automated fluorescent cell counter.

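### Primary safety outcome (a) has no rule for counting serious events outside six named items, and no safety set covers patients excluded after liposuction

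*Combined protocol and SAP*

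**What the plan says.** Safety is specific objective (i) in Section 3.2. In Section 4.11.1 it becomes primary outcome (a), the incidence of minor adverse events and "serious adverse events (SAEs) which may be immediate, early or late - for Phase I", with a time frame of week 48.

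- **Minor events, four items:** prolonged liposuction pain ("Pain from lipo-suction > 7 days (Early"), fever beyond 7 days, subcutaneous haematoma or abscess, and allergic reaction.
- **Serious events, six items:** anaphylaxis, pulmonary embolism or infarction, new neoplasia, new cardiovascular events, new cerebrovascular or neurological events, and reactivated tuberculosis. Each is tagged immediate or late.

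Criterion 15 of Section 4.8.2 (also stated in Section 4.1) removes patients whose harvested "count (in 5 ml SVF solution) less than 1 x 10 6 will be excluded from the study". The count is taken in the last step of Section 7, just before infusion: "Before that to collect few drops of SVF sample for cell counting". Section 7 also sets a viability condition, "The final SVF is ready for subcutaneous or IV injection if 80-90% of cell remain viable, active and mobile", and does not say what happens to a patient whose cells fail it.

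On numbers, Section 4.1 has "Enrollment: 31 [Anticipated", Section 6.3 says "According to sample size calculation 31 patients with established CKD will be recruited in the study over the estimated study period", and Section 4.7 says "The recruitment will be continued till the desired sample is drawn". Section 4.15 (Data analysis) names no safety population.

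**The concern.** A Phase I safety result should account for every serious event in everyone exposed to a study procedure. Outcome (a) leaves two gaps.

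The main one is what counts as serious. The only definition is a list of diagnoses. The patients are aged 18 to 80, have CKD stage 3 to 5 and are followed to week 48, so serious events outside six diagnoses are plausible. Whoever tabulates outcome (a) would have no rule for including, for example, a death from sepsis or a hospital admission for an abdominal complication. The abscess or fever behind a serious infection would be tabulated as minor.

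The second gap is who is counted. Outcome (a) includes harms of the harvest itself, but low-yield patients leave the study after they have had the harvest. Their injuries may never reach the primary safety table.

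**Working it through.** **1. Do the serious-event rules cover an unlisted event?** Section 4.11.1 was set against possible serious events:

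| Event | Route into outcome (a) |
|---|---|
| Death or admission from a cardiovascular, neurological, neoplastic or other listed cause | Through the listed item |
| Death or admission from any other cause | None stated |
| Systemic infection other than reactivated tuberculosis | Fever beyond 7 days or abscess, both minor |

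Three of the six items are broad, so many serious events are covered. The remainder is not.

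**2. Would the data exist?** Largely yes. Questionnaire 1 (Annexure C) records symptoms such as fever, respiratory distress and chest pain, with an open field for others, at all visits. Questionnaire 2 records antibiotics, analgesics and other medicines at all visits. Annexure D has a blood count at each scheduled visit. No text says that anything recorded there counts in outcome (a). The gap is in classification and counting more than in data collection.

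**3. How likely is an unlisted serious event?** The protocol gives no rate, so the risk p by week 48 is assumed. With 31 patients, P(at least one) = 1 − (1 − p)^31:

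| p | 0.5% | 1% | 2% | 5% | 10% |
|---|---|---|---|---|---|
| P | 14% | 27% | 47% | 80% | 96% |

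This is the chance that such an event occurs, not that it goes unreported.

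**4. What does 31 count?** The plan's own figure (Section 4.6) is N = AB/C = 1.000 × 7.849 / 0.250 = 31.4, given as about 31. It is sized on the standard deviation of a change in outcome, so it refers to patients with a post-treatment measurement. Section 4.9 has all subjects treated. Section 4.7 recruits against the eligibility criteria until the sample is complete, and a low count is an exclusion criterion. These favour 31 infused.

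**5. How many harvested patients could fall outside?** The low-yield share f is assumed. Harvests needed = 31/(1 − f), rounded up:

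- f = 10%: 34.4, so 35 harvested and 4 outside
- f = 20%: 38.75, so 39 harvested and 8 outside
- f = 30%: 44.3, so 45 harvested and 14 outside

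If each harvest carries a 5% event risk (assumed), the chance of at least one event among those outside is 1 − 0.95^m with m = 4, 8 or 14, that is 19%, 34% or 51%.

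**6. Does this move the rate?** Illustration with f = 20%: 3 harvest events among 31 infused is 9.7% (exact 95% CI 2.0% to 25.8%). Adding the 8 others with 0, 1 or 2 events gives 3/39 = 7.7%, 4/39 = 10.3% or 5/39 = 12.8%. All lie inside that interval, on either side of 9.7%.

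**The case against.** The strongest reply is that the six items are never called exhaustive. Outcome (a) is worded as the incidence of adverse events in general, and the items can be read as examples. That stands as far as it goes: a reader might infer that an unlisted death is definitely not a serious adverse event under this plan, and the text does not say so. What it supports is that such a death is not clearly one, because no criterion or open item brings it in.

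A reader might also infer that an embolism some days after the procedure is lost because the item is tagged immediate. The tags read more naturally as expected onset, nothing says an event outside its tag is dropped, and the time frame runs to week 48. The undefined windows are a reporting gap only.

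It can be said that the questionnaires and blood counts would reveal a serious infection. They would leave traces, but no rule carries those traces into the primary outcome.

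On the harvested patients, the effect on the rate is small and the listed harvest items are tagged early, so year-long follow-up of patients who were not infused is not needed to capture them. Both points are accepted. The consent annexure is not part of the text reviewed, so the statement that no follow-up is provided for these patients is limited to the visible sections.

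**Conclusion.** The concern holds, and the serious-event definition carries most of its weight. Followed as written, the plan can leave an unlisted death or hospitalisation out of its Phase I primary result, or show a serious infection only as a minor event. That should be corrected before the safety result is relied on. The 14% to 96% range rests wholly on assumed risks and shows only that such an event need not be rare in 31 patients.

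The post-harvest exclusion is secondary. Some 4 to 14 patients may have liposuction without their harms being counted, if the low-yield share is 10% to 30% and 31 are infused. The issue is complete capture of harms; the documents do not support a claim that the reported rate is materially biased, or biased in a known direction. Nor is the meaning of 31 seriously in doubt: the text favours infused patients, and one confirming sentence is enough.

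**What to change.** **Serious events (Section 4.11.1).**
- Define a serious adverse event by standard seriousness criteria: death, life-threatening, hospitalisation or its prolongation, disability, or medically important, at any time to week 48.
- Keep the six items as events of special interest.
- State that the immediate, early and late tags are descriptive only.
- State that any qualifying event recorded at a visit counts in outcome (a), including events entered in the open field of Questionnaire 1.

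**Safety set (Sections 4.8.2 and 4.15).**
- Leave criterion 15 as the rule for Groups A and B and for efficacy.
- Define the safety set for harvest events as all consented patients who start liposuction, including those not infused because of a low count or failed viability.
- Follow patients who are not infused long enough to capture the listed harvest events. The pain and fever items cannot be judged until more than 7 days have passed.
- Report the harvest-failure proportion, harvest events among all harvested, and infusion events among all infused, each on its own denominator with an exact 95% CI.
- Add one sentence confirming that 31 means infused patients.

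**Cost.** Amendment wording, an event form, and short safety follow-up of a few extra patients (about 4, 8 or 14 under the assumed shares). The reported event count may rise. No cell threshold or treatment rule changes.

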#### 4.9 Treatment allocation

All subjects would be submitted for Stromal Vascular Fraction (Autologous Adipose Derived Mesenchymal Stem Cell) Based Treatment for Chronic Kidney Disease

#### 4.10 Pre-transplant and Post-Transplant Investigations

Investigations will be done according to the Annexure – D

#### 4.11 Outcome measures

#### **4.11.1 Primary Outcome Measure**

a) Incidence of minor adverse events (MAEs), serious adverse events (SAEs) which may be immediate, early or late - for Phase I [Time Frame: Week 48]

Minor adverse events (MAEs):

i) Pain from lipo-suction > 7 days (Early)

- ii) Fever > 7 days (Early)
- iii) Subcutaneous hematoma / abscess formation (Early)
- iv) Allergic reaction (Immediate)

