3.1 General Objective

To assess the outcome of stromal vascular fraction (autologous adipose derived mesenchymal

stem cell) based treatment as a new, safe and minimal invasive modality for the treatment of

chronic kidney disease.

3.2 Specific Objectives:

(i) To assess the safety of stromal vascular fraction (autologous adipose derived mesenchymal

stem cell) in the treatment of CKD

(ii) To determine the role of SVF in treating different stages of CKD

(iii) To see if SVF can reverse or limit the progression of CKD

4. Methodology

The study will be conducted considering following methodological aspects.

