#### 4.6 Sample size determination:

 $\alpha$  (two-tailed) = Threshold probability for rejecting the null hypothesis. Type I error rate.

 $\beta$  = Probability of failing to reject the null hypothesis under the alternative hypothesis. Type II error rate.

E = Effect size

 $S(\Delta)$  = Standard Deviation of the change in the outcome.

Here,  $\alpha = 0.05$ 

 $\beta = 0.20$ 

E = 0.5

 $S(\Delta) = 1.0$ 

The standard normal deviate for  $\alpha = Z_{\alpha} = 1.960$ 

The standard normal deviate for  $\beta = Z_{\beta} = 0.842$ 

A = 1.000

$$B = (Z_{\alpha} + Z_{\beta})^2 = 7.849$$

$$C = (E/S(\Delta))^2 = 0.250$$

Sample size N = AB/C = 31 (approx.)

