#### 4.15 Data analysis

The edited data will then be entered on to the template of SPSS® 16 and STATA® 10/IC.

For Back ground variables and socio-demographic data descriptive statistics and relative frequency (percentage) will be generated.

Through univariate analysis the base line characteristics and treatment outcome will be compared. The effect of treatment will be identified through Multivariate analysis after adjusting for possible confounders. Relative risk with 95% CI will be generated through binary logistic regression adjusting for all possible confounders.

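### The primary safety outcome has no stated denominator, and patients excluded for a low cell count after liposuction drop out of it together with their harvest-related events

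*Combined protocol and SAP*

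**What the plan says.** Safety is the first specific objective (3.2), and the general objective (3.1) describes the treatment "as a new, safe and minimal invasive modality". Primary outcome (a) in 4.11.1 is "Incidence of minor adverse events (MAEs), serious adverse events (SAEs) which may be immediate, early or late - for Phase I", with a week 48 time frame. The minor events listed are liposuction pain beyond 7 days, fever beyond 7 days, subcutaneous haematoma or abscess, and allergic reaction. The serious events run from anaphylaxis and pulmonary embolism to late neoplastic, cardiovascular and neurological events. No denominator, safety population, interval or reference rate is given.

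Section 4.1 and criterion 15 in 4.8.2 say that patients whose harvested count is below 1 x 10^6 "will be excluded from the study". Section 7 takes the sample for counting after liposuction, digestion and washing, just before the infusion. Section 4.1 says that Groups A and B are studied on the outcome measures, and 4.2 says that both are infused. No adverse event recording is described for a patient excluded at the count.

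The only interval named in 4.15 is in this sentence: "Relative risk with 95% CI will be generated through binary logistic regression adjusting for all possible confounders". Section 4.16 plans frequency tables for descriptive results.

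**The concern.** Criterion 15 is not an ordinary screening failure. It depends on the result of a study procedure that the patient has already undergone, and that procedure can itself cause events on the primary safety list. A patient who has liposuction, falls below the count and then has pain for more than 7 days has a listed event, yet under the plan belongs to neither group and so to no analysis.

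At stake is the Phase I result for the whole intervention, which is harvest plus infusion. Its harvest component would be estimated only in patients whose harvest succeeded. If a difficult harvest both yields few cells and causes more local harm, the incidence is biased downward. If the two are unrelated, information is still lost and the reported denominator is not the number exposed to liposuction.

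A second, lesser gap is precision. With about 31 patients a low or zero count is compatible with rates that matter, and the plan does not say that an incidence will carry an interval.

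**Working it through.** **1. The plan's own figure.** Section 4.6 uses a two-tailed alpha of 0.05, beta of 0.20, effect size 0.5 and SD of the change 1.0. Then (1.960 + 0.842)^2 / (0.5/1.0)^2 = 7.849/0.250 = 31.4, which the plan gives as approximately 31 (strict rounding up gives 32). This figure comes from a mean change. It has no link to an adverse event rate, so it does not say what 31 patients can show about safety.

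**2. Who is in the safety result.** The steps in order are:
- liposuction, processing and cell count (section 7);
- exclusion if the count is below 1 x 10^6 (4.1; 4.8.2, criterion 15);
- assignment to Group A or B by count (4.1);
- infusion of both groups (4.2);
- outcome measures in both groups (4.1).

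The exclusion falls between harvest and infusion, so a harvested-but-excluded patient is exposed to liposuction but has no place in the outcome analysis.

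**3. How many patients.** The plan gives no failure rate f, so 10% to 30% is assumed. It also does not say whether the 31 are counted before or after this exclusion, so both readings are shown.

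| Reading of 31 | f = 10% | f = 30% |
|---|---|---|
| 31 infused: harvests = 31/(1 - f), rounded up | 34.4, so 35 | 44.3, so 45 |
| Liposuction patients left out | 4 | 14 |
| 31 harvested: infused = 31 x (1 - f) | 27.9, about 28 | 21.7, about 22 |
| Liposuction patients left out | 3 | 9 |

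**4. Effect on an incidence (hypothetical).** Take the first reading with f = 10%, no harvest event among the 31 infused and one among the 4 excluded. The plan would report 0/31. Over all patients who had liposuction it is 1/35 = 2.9% (exact 95% interval 0.1% to 14.9%). With f = 20% (38.75, so 39 harvests) and two events among the 8 excluded, 0/31 becomes 2/39 = 5.1% (0.6% to 17.3%).

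**5. Precision.** With zero events the exact (Clopper-Pearson) two-sided 95% upper limit is 1 - 0.025^(1/n).

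| n | Upper limit |
|---|---|
| 31 | 11.2% |
| 28 | 12.3% |
| 22 | 15.4% |
| 16 | 20.6% |
| 15 | 21.8% |

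The one-sided 95% limit at n = 31 is 1 - 0.05^(1/31) = 9.2%, so the convention must be named. With 1/31 the two-sided interval is 0.1% to 16.7%, and with 2/31 it is 0.8% to 21.4%. At a true rate of 5%, the chance of no event in 31 is 0.95^31 = 20.4%.

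**The case against.** The strongest reply is that 4.11.1(a) nowhere restricts incidence to infused patients; it is silent. That is correct. The restriction is an inference from 4.1, 4.2 and 4.8.2 read together. Nothing in the document contradicts it, but the accurate charge is that the denominator is undefined and that following the other sections leaves these patients out.

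A reader might also infer that zero events in 31 will be declared safe. The document does not say so. The word in 3.1 belongs to an objective, 3.2 speaks of assessing safety, and no success criterion exists. Likewise, a reader might take the relative risk in 4.15 to be the planned adverse event analysis, and object that it cannot be fitted. Section 4.15 does not assign that model to adverse events: it follows a sentence on the effect of treatment, and the frequency tables of 4.16 could carry the incidences. With no events such a model has nothing to estimate. With a few it may fit but be unstable. Neither shows that the plan's safety analysis fails.

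It can further be said that anyone can compute an exact interval from a count and a denominator. This stands in part: the interval is mainly a reporting gain. It does not answer the main point, because no reader can recover events that were never recorded.

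Finally, only liposuction pain is tied to the harvest by name. Attributing haematoma or abscess to it is plausible but inferred, and fever, allergic reaction and pulmonary embolism could be placed in either phase. That is a reason to name a set for each event.

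**Conclusion.** The point holds for the denominator. Following the plan as written, patients excluded at the cell count have had liposuction, can have events on the primary safety list, and are not counted. Under an assumed 10-30% failure rate, 4 to 14 such patients are left out if 31 are infused. If the 31 are counted before exclusion, about 28 to 22 are infused and the remaining 3 to 9 are left out. The failure rate is an assumption, and the meaning of 31 is open in the document.

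The missing interval is a secondary weakness. The 11.2% limit applies only if 31 is the infused number; it is 12.3% to 15.4% under the other reading. A statement by group would face about 21-22%, assuming a near-equal split that the plan does not fix. The documents do not support the stronger claims that safety will be declared on zero events or that a logistic model is the planned safety analysis. The gap should be closed, but it does not invalidate the trial.

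**What to change.** - **4.8.2 (15) and 4.11.1(a):** keep every patient who undergoes liposuction in a harvest safety set, including those who then fall below the count, and record the listed early events in them. Follow-up must be long enough to see events defined by lasting more than 7 days; the existing week 2 or week 4 visit would serve.
- **4.11.1(a):** report harvest-related events over the harvest safety set, and infusion-related and late events over all infused patients. Name the set for each listed event, including those that could belong to either phase.
- **4.1 and 4.6:** state whether the 31 are counted before or after the cell-count exclusion.
- **4.15:** add an exact (Clopper-Pearson) 95% interval to each adverse event incidence. State the zero-event upper limit for the actual denominator, pooled and, if a group statement is made, by group.

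The cost is a short adverse event follow-up of patients harvested but not infused. This is a small change to data collection as well as to the analysis text. It needs no more infused patients and no change to treatment. The safety statement will probably read less favourably.

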#### 4.5 Study population:

Patient of CKD who fulfill the selection criteria and admitted at the selected health facility for treatment.

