#### Serious adverse events (SAEs)

- i) Anaphylaxis (Immediate)
- ii) Pulmonary embolism or infarction (Immediate)
- iii) Outset of any neoplastic change (Late)
- iv) Outset of new Cardiovascular events (Late)
- v) Outset of new Cerebrovascular or neurological events (Late)
- vi) Reactivation of treated tuberculosis (Late)
- b) Change from baseline to 24 week visit in estimated glomerular filtration rate (eGFR) and split renal function in all patients for Phase II [Time Frame: Weeks 0, 24]
  - eGFR with split renal function will be evaluated using DTPA Renogram.
- c) Change from baseline to 24 week visit in estimated glomerular filtration rate (eGFR) with serum creatinine level in patients with CKD 4 and below for Phase II [Time Frame: Weeks 0, 2, 4, 12, 24]
  - eGFR will be calculated by Serum Creatinine level using MRDR formula during all visits.
- d) Change from baseline to 24 week visit in need for dialysis in patients with CKD 5 for phase II [Time Frame: Weeks 0, 2, 4, 12, 24]

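### Primary safety outcome (a) is specified by ten named events, with no rule for which other events count and no outcome-based definition of serious

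*Combined protocol and SAP*

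**What the plan says.** Specific objective (i) in section 3.2 is "To assess the safety of stromal vascular fraction" in CKD. The matching endpoint is primary outcome (a) in section 4.11.1, assigned to Phase I with a week 48 time frame: "Incidence of minor adverse events (MAEs), serious adverse events (SAEs) which may be immediate, early or late".

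Two numbered lists follow.

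- **Minor (4):** liposuction pain lasting beyond 7 days; "Fever > 7 days (Early"; "Subcutaneous hematoma / abscess formation (Early"; allergic reaction.
- **Serious (6):** anaphylaxis; pulmonary embolism or infarction; "Outset of any neoplastic change (Late"; new cardiovascular events; new cerebrovascular or neurological events; "Reactivation of treated tuberculosis (Late".

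Neither list has an entry for other events. Neither is introduced as examples or said to be complete. Section 4.15 (data analysis) adds no rule for adverse events, and the table of contents shows no safety section and no adverse-event form.

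Related data are planned elsewhere. Questionnaire 1 (Annexure C) records symptoms, temperature, dialysis score and other findings at all visits, and Questionnaire 2 records medicines. Section 4.12 plans a checklist drawn from hospital, treatment and laboratory records. Section 4.11.2 covers hypoglycaemia, transfusion and tumour markers, and Annexure D lists the laboratory tests. None of these is linked to outcome (a).

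**The concern.** Seriousness is fixed by the name of the event, not by its consequence for the patient. A result that matters greatly for safety can therefore fall outside the endpoint or be graded minor within it. Safety is both a specific objective and the Phase I primary outcome, so a low count on outcome (a) could be read as evidence of general safety when it describes only the ten chosen events. If the lists are only examples, the problem changes form: two assessors could classify the same unlisted event differently, and the choice could be made after the event is known.

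**Working it through.** The plan states no figure for this outcome. Its only calculation, the sample size of 31 in section 4.6, is for a change score and does not bear on the point. The check is a count and a side-by-side reading.

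**1. Count the items (section 4.11.1).** Minor 4 + serious 6 = 10. Catch-all entries: 0. Criteria that decide seriousness by outcome (death, threat to life, hospitalisation, disability): 0. Items with a duration cut-off: 2 of 10 (pain and fever, both beyond 7 days).

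**2. Apply the lists as written to test cases.**

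| Event | Item matched | Grade |
|---|---|---|
| Death or hospitalisation, cause outside the lists | none | not counted |
| Death or hospitalisation from a new cardiovascular, cerebrovascular, neurological or neoplastic event | that cause | serious |
| Systemic infection, fever beyond 7 days | fever item | minor |
| Systemic infection, shorter or no fever, not reactivated tuberculosis | none, unless it leads to another listed event | not counted |
| Reactivated treated tuberculosis | tuberculosis item | serious |
| Subcutaneous abscess leading to hospitalisation | abscess item | minor |

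**3. Apply the other reading.** If the lists are examples, rows 1 and 4 might be counted. The text then has to say which unlisted events qualify and which are serious, and it does not.

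**4. Check whether the planned data close the gap.** Questionnaire 1 has fever and pain as yes or no, without a duration, so the form alone cannot show whether either 7-day cut-off was met. No supplied form or checklist item visibly records death, admission, onset, duration or seriousness. The hospital-record checklist might contain such information, but its items are not given.

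**5. Scale, under assumed rates only.** Let p be the risk per patient, over 48 weeks, of a serious event outside the lists. The documents give no value for p. With 31 independent patients, the chance of at least one such event is 1 − (1 − p)^31:

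- p = 2%: 1 − 0.98^31 = 46.5%
- p = 5%: 1 − 0.95^31 = 79.6%
- p = 10%: 1 − 0.90^31 = 96.2%

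This shows how readily the question could arise in a trial of this size. It does not estimate how much harm would be missed.

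**The case against.** The strongest reply is that the opening phrase of outcome (a) is general and nothing makes the lists exhaustive, so unlisted events may have been meant to count. This stands in part: undercounting follows on only one of the two readings. It does not rescue the endpoint, because the general reading has no rule for inclusion or seriousness.

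A second reply is that the serious items are broad. This also stands. Any neoplastic change and new cardiovascular, cerebrovascular or neurological events are covered, so the deaths and admissions left out are only those from other causes.

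A third is that much safety information is collected anyway. That is true of symptoms, medicines, laboratory results and records, and some unlisted events could be recovered from them. They are not tied to outcome (a), however, and the key fields noted in the working are not visible on any form.

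A fourth is that ignoring fever of 7 days or less is a reasonable threshold for a minor event. It may well be deliberate, and it is not a gap comparable with an uncounted death.

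**Conclusion.** The point holds. Outcome (a) lacks a general definition of an adverse event, an outcome-based definition of serious, and a statement of whether its lists are complete. On either reading it cannot carry objective (i) alone. The defect lies in definition and linkage, and the number of events affected cannot be estimated from the documents. The conclusion assumes that no adverse-event definition sits in pages removed from the public file; nothing in the supplied text points to one.

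A reader might infer more than the text supports:

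- **That harm will be understated.** This follows only if the lists are applied as exhaustive, which the plan does not say.
- **That systemic infection is never counted.** It is counted if fever lasts beyond 7 days, though as minor, or if it is reactivated tuberculosis.
- **That no safety data are collected.** Several sources are planned.
- **That serious events in the early period are excluded.** None of the six serious items carries the early label, but the labels have no time windows and no section uses them to restrict counting.

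**What to change.** Reword outcome (a) in section 4.11.1 as any adverse event through week 48. Call an event serious if it results in death, is life-threatening, causes or prolongs hospitalisation, leaves lasting disability, or is otherwise medically important. State that the planned treatment admission does not itself qualify, since section 4.5 describes patients "admitted at the selected health facility for treatment". Keep the ten items, with their own cut-offs, as events of special interest reported separately. Name Questionnaires 1 and 2 and the hospital-record checklist as sources, and add one adverse-event page recording death, admission, onset and duration. Report the number of patients with at least one event and the number with at least one serious event.

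The cost is protocol wording plus a small but real data-collection burden. Visits at weeks 4, 12, 24, 36 and 48 leave gaps of 8, 12, 12 and 12 weeks, so recall of onset and duration will be imperfect. The event count will rise and will include events from CKD progression: section 4.9 says "All subjects would be submitted for Stromal Vascular Fraction", so there is no untreated comparator to separate them. That is why the special-interest items should be shown on their own. Treatment and sample size do not change.
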